 6. We will send participants a RedCap survey link through text message or email 30 days and 60 days after the intervention to assess intent to be vaccinated for COVID-19 and vaccine uptake, allowing time for both doses of the Pfizer and Moderna, single dose of Jansen's COVID-19 vaccine, or boosters of vaccines to be delivered. We will also send up to three daily reminders to the participant to complete the common data elements survey if they did not complete it after the intervention.
 7. For participants who agree, we will contact up to 60 participants to participate in an evaluation interview to help the personnel determine what did and did not work well during the intervention. This will be a 30 minute to one hour interview.

At all events, key personnel will also conduct a field observation of how the events flow, including external factors such as weather or logistical problems and where challenges to implementing the study or recruiting participants occurred. We will also conduct evaluation focus groups with event site staff to determine what did and did not work during the event.

We expect to recruit 2000 participants over the entire study period (Aim 2.1 and 2.2).

Factorial design. In a factorial research design, two or more independent variables are concurrently examined within the same trial. The three factors are crossed with one another to create a total of eight experimental conditions. An equal number of participants are randomly assigned to each condition, using a random number generator. This is not an 8-arm randomized controlled trial, but instead allows for an efficient examination of main effects for each variable in a sample of 2000 participants (including Aim 2.1 and Aim 2.2).

This approach allows examination of three key treatment development questions in a much more time-efficient and economical manner by simultaneously performing three studies within the single trial. This achieves power to detect between-group differences that is equivalent to performing three separate randomized trials. Investigators who are providing the intervention and conducting analysis will be not be masked to study assignment due to challenges in maintaining the masking in an educational intervention. For all sites, including Aims 2.1 and 2.2, we expect to recruit 2000 participants.

Identifiers might be removed and the de-identified information may be used for future research without additional informed consent from the subject.

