Evaluation. Global questions will be explored in the program evaluation, including: 1) What are potential barriers and facilitators to “real-world” implementation of the interventions?; 2) What problems are associated with delivering the interventions, and how might they translate to improving implementation processes?; 3) What potential modifications to the interventions could be made to maximize implementation?; and 4) Among the interventions that were implemented, which appeared most promising? *Implementation process metrics* will be assessed by conducting a process evaluation for deployment of interventions to increase vaccine uptake. To organize process findings, we will generate a comprehensive list of patient and community implementation outcomes aggregated through the common taxonomy of the Proctor et al. evaluation framework.^{11, 12} The evaluation also will incorporate measures from CFIR,¹³ which has been shown to be effective for guiding successful implementation.^{14, 15}

Research team members will visit the community sites or meet through videoconference to conduct five additional focus groups with multiple respondents, including the community members involved in the intervention, to assess acceptability, cultural relevance, and possible barriers. We will also interview participants who agreed to an interview in the consent form for evaluation of the intervention. Findings will help clarify processes of care and perceptions of barriers and facilitators. The focus group guide will prompt participants to discuss their practice context as it relates to their experiences with implementing each of the intervention components, and participants will be probed regarding challenges and facilitators they face when implementing each component. To evaluate whether the selected intervention(s) improved vaccine uptake in the pilot study, our team will evaluate aggregate vaccination data for the catchment area of the community site through the Oklahoma State Department of Health. The final product will summarize barriers and facilitators for implementation and provide a thorough picture of the implementation process, including feasibility, acceptability, and fidelity of intervention implementation that can inform future large-scale research.

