Recruitment: We will recruit sites through the CATCH-UP program testing events and as requested through community partnerships in collaboration with the Public Health Institute of Oklahoma. We will recruit through flyers, emails, and direct contact during events. Participants will be eligible for a \$20 gift card at the completion of the study, which will either be given to participants on-site, mailed to the participants, or emailed as an e-gift card.

Consent Procedures: After completing a screening form, eligible participants who are interested in the study will review and sign the consent and HIPAA authorization form if they decide to participate in the study. The consent form will include questions about sharing zip code with the Duke Clinical Research Institute and contact for future research studies. Study staff will review the consent form and answer any questions. Consent and HIPAA authorization will be conducted either with paper forms or electronically through REDCap.

Location where consent and intervention will take place: We will conduct the intervention at multiple community events, which will be open to the public, as identified by community organizations as they are scheduled in partnership with PHIO.

Measures to decrease participant coercion: Potential participants will be notified through the consent process that participating is optional and withdrawing from the study any time is allowed. Study personnel will not be supervisors of any potential participants.

Aim 2 Evaluation with intervention event staff/volunteers

Recruitment: Focus groups will include community leaders and staff/volunteers involved in community events where CATCH-UP Vaccines interventions were held. We will work with [name] at Public Health Institute of Oklahoma to assist with recruitment of focus group participants. We will recruit focus group participants through emails and advertisements to the community organizations and will use REDCap to register interested potential participants. If a participant recommends including other potential participants in future focus groups, we will provide the participant with the study team's contact information to allow any potential participants to obtain more information about the study while maintaining confidentiality between participants.

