COVID-19 incidence, particularly among underserved minority and rural Oklahomans. Oklahoman's are also reporting SARS-CoV-2 vaccine hesitancy and signs of slowing vaccine uptake, with increased hesitancy among American Indian and rural populations. The project aims to work with ongoing community testing events to implement interventions to improve vaccine uptake among Oklahoma's underserved populations.

I. Statistical Methods

Aim 1 Analysis. Digitally recorded focus groups will be securely uploaded to protected servers and transcribed using NVivo Transcription. Transcriptions will be team coded for conceptual themes using QSR NUDIST Vivo12 Pro for Windows.¹⁶ Investigators will develop a code book. Throughout the coding process, qualitative data will be categorized, connections made between categories, and core categories identified and systematically linked to other categories. Focus group data will inform intervention selection and needed modifications for community acceptability/relevance.

Aim 2 Analysis. All analyses are intent-to-treat. Outcome measures will be assessed at baseline, 30 days, and 60 days follow-up. At the outset, we will examine the frequency distributions of all variables. We will compare the baseline characteristics to assess whether randomization distributed covariates evenly. We will determine whether there is differential dropout and consider developing probability-of-completion weights to obtain unbiased estimates of treatment effect.

The primary analysis will assess the effects of each intervention component in terms of its association with the primary outcome (intent to receive a COVID-19 vaccine immediately after the interventions are completed). Cross-sectional analyses will be conducted for outcomes assessed at 30 and 60 days. For binary outcomes, chi-square tests will be used to compare the outcomes between groups. For continuous outcomes, two-sample t-tests or Wilcoxon rank sum tests, whichever is more appropriate, will be used to compare between groups. A longitudinal analysis using Generalized Estimating Equations (GEE) techniques will also assess the overall impact of the intervention by including data from all follow-up time points.

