As a secondary analysis, we will compare vaccine coverage among counties with an intervention compared to counties without intervention to see whether coverage increased in the study counties using a chi-square test. We will use publicly available data from the Oklahoma State Department of Health and/or Centers for Disease Control and Prevention for this analysis.

Sample size and power calculations. Power calculations are based on our primary analysis, which is to assess the effect of each intervention component on increased intention to receive a COVID-19 vaccine immediately after the intervention. This is a two-sample comparison between participants that receive one intervention component and those that receive the control. Our pilot implementation will include a single site with an estimated 500 participants.

Our outcome of interest is also assessed at 30 and 60 days follow-up to measure intention to receive a COVID-19 vaccine, which allows us to use a longitudinal generalized estimating equations approach wherein power is proportional to the within-site

correlation. Using PASS v16, we assume the intra-cluster correlation within each site is 0.01. Our power analysis is based on data from both pilot and full implementation of the study results. Assuming a minimum n=167 participants per site for a minimum of sites, a Type 1 error rate of 0.05, and an estimated standard deviation of 5, we have over 80% power to detect a mean difference of 20.

Data and Safety Monitoring Plan

Drs. [name] and [name] assure that oral informed consent is obtained prior to conducting the focus groups (Aim 1) and written informed consent and HIPAA authorization are obtained for the intervention (Aim 2) prior to performing any research procedures, that all subjects meet eligibility criteria, and that the study is conducted according to the IRB-approved research plan.

Study data are accessible at all times for the PI/PD to review. [name] will review the study conduct weekly and the PI/PD will review the study conduct on a monthly basis. Study conduct will include accrual, drop-outs, and protocol deviations. The PI/PD will review adverse events individually in real-time and in aggregate on a weekly basis.

COLLECTION AND REPORTING OF SAEs AND AEs

For this study, the following standard AE definitions are used:

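### The county chi-square has no baseline, on its natural reading counts residents rather than counties, and compares non-randomised counties, so it cannot show that coverage increased and would often be significant with no effect

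*Combined protocol and SAP*

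**What the plan says.** Section I (Statistical Methods) adds a secondary analysis of coverage in "counties with an intervention compared to counties without intervention to see whether coverage increased in the study counties using a chi-square test". On the source it says only: "We will use publicly available data from the Oklahoma State Department of Health and/or Centers for Disease Control and Prevention for this analysis". It gives no dates, pre-intervention period, dose measure, change measure, unit of analysis, clustering term or adjustment. The baseline mentioned earlier in Section I belongs to the Aim 2 outcome measures collected from participants.

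The Evaluation part of Section D makes a related statement: "To evaluate whether the selected intervention(s) improved vaccine uptake in the pilot study, our team will evaluate aggregate vaccination data" for the site's catchment area. It names no comparator or pre-period.

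The design sections show what was randomised. Under Factorial design in Section D, individual participants are assigned to conditions. Counties are not assigned. Section G, Aim 2.2, says of the sites: "We will recruit sites through the CATCH-UP program testing events and as requested through community partnerships". The interventions take place at "multiple community events, which will be open to the public, as identified by community organizations as they are scheduled".

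The plan also has a randomised source of information on uptake. Participants are surveyed "30 days and 60 days after the intervention to assess intent to be vaccinated for COVID-19 and vaccine uptake", and Section I compares these outcomes between randomised groups.

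**The concern.** The stated question is whether coverage increased. A chi-square of vaccinated against unvaccinated residents by county group answers a different one: whether the two groups have the same level of coverage.

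Three faults combine.

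- **No baseline.** Counties that already differed before the first event will still differ afterwards. Section H reports "signs of slowing vaccine uptake, with increased hesitancy among American Indian and rural populations", so a pre-existing gap is plausible if events are held mainly in such areas. The documents do not give its size or direction.
- **Wrong unit.** Residents of one county share access, outreach and attitudes. The test treats millions of residents as independent, although the comparison rests on a modest number of counties.
- **No randomisation of counties.** Sites come from existing events and community requests, so the choice of county may be linked to its coverage or its trend.

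The statement in the Evaluation part has a further problem. Participants at the same event are randomised individually to different conditions, so catchment totals cannot tell one intervention component from another.

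At stake is a misleading county-level statement, in either direction, about vaccine uptake, which is the behaviour the project aims to change.

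**Working it through.** The plan gives no figure for this analysis, so there is none to reproduce.

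**Inputs from the documents.** Section B gives 2.6 million doses, 38% of the population with one dose and 30% fully vaccinated. Section D gives 2000 participants. Alpha is 0.05 in Section I, stated for the primary power calculation and taken here as two-sided.

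**Assumptions.** 10%, 15% or 30% of residents live in study counties. There are 60 counties with 9 holding events, or 80 with 12. County sizes are log-normal with log-SD 0.5 to 1.2. The between-county SD of coverage is shown as a range.

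**1. Population.** Counting one dose for the 38% and a second for the 30%: 2.6 million / (0.38 + 0.30) = 3.82 million.

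**2. Smallest significant gap.** Threshold = 1.96 × sqrt[0.38 × 0.62 × (1/n1 + 1/n2)], where n1 and n2 are the residents in study and other counties. Extra vaccinations needed = threshold × n1.

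| Share in study counties | n1 | Threshold (points) | Shift from 200 extra vaccinations (points) | Extra vaccinations needed |
|---|---|---|---|---|
| 10% | 382,353 | 0.162 | 0.052 | 620 |
| 15% | 573,529 | 0.136 | 0.035 | 781 |
| 30% | 1,147,059 | 0.106 | 0.017 | 1218 |

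The 200 stand for 10% of the 2000 participants newly vaccinated because of the study (assumed). Reaching the threshold would take 31% to 61% of all 2000 (620/2000 and 1218/2000).

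**3. Rejection rate with no effect.** Counties are simulated around 38% coverage with 3.82 million residents in total, and residents are pooled into a chi-square (4000 runs per cell).

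| Between-county SD (points) | Significant | Significant in favour of study counties |
|---|---|---|
| 0.25 | 22-38% | 10-19% |
| 0.5 | 48-62% | 24-31% |
| 1 | 70-80% | 36-40% |
| 3 | 90-93% | 45-47% |
| 5 | 94-96% | 47-49% |

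A second model, with 3 to 20 study counties and median county sizes of 5,000 to 40,000, gives 4-5% at SD 0, 16-57% at 0.5, 36-76% at 1 and 84-95% at 5.

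**4. A pre-existing gap.** If study counties start 1 point lower (assumed; SD 0.5 to 3) and nothing happens, the chi-square reports significantly lower coverage there in 70-100% of runs.

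**5. Other readings of the sentence.**

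- A before/after chi-square within study counties has threshold 1.96 × sqrt(2 × 0.38 × 0.62 / n1) = 0.218, 0.178 and 0.126 points for the three shares. Any statewide rise above that would be credited to the study.
- A chi-square on newly vaccinated counts has a baseline but still ignores county-to-county variation. With an SD of change of 1 point it rejects in 84-91% of runs with no effect.
- A table of counties by whether coverage rose is not described. It would say little, because cumulative coverage rises almost everywhere.

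**6. County as the unit.** With an SD of change of 1 point and no effect:

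- unweighted two-sample t-test on county change: rejects in 4.1-5.9%
- permutation test: 3.9-5.9%
- unweighted regression adjusted for pre-period coverage: 4.1-6.3%
- population-weighted regression with robust errors: 7.0-16.7% (HC1) or 5.1-8.3% (HC3)

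Under the 1-point starting gap in step 4, the t-test on change stays at 3.9-6.4%.

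**The case against.** The strongest reply is that the plan never names the unit, so the fault is missing detail and not a wrong test. The simulated rates also rest on county numbers and SDs that the documents do not give. The 38% is a first-dose figure from April 2021, whereas the eligibility criteria follow recommendations of April 2023 and concern bivalent doses. Spillover to people who attend the public events without enrolling is not counted. Finally, this is one sentence labelled secondary; county coverage is not a listed outcome.

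Parts of this stand. Counting residents is an inference, although it is the natural reading of a chi-square on coverage. The exact rates depend on the assumed SD, and the second model shows a wider spread. The count of 620-1218 vaccinations is tied to 38% coverage: at 5-10% coverage (assumed) the threshold falls to 0.05-0.10 points and 278-752 vaccinations. Spillover could make the true effect larger than 0.02-0.05 points. The Evaluation section does not say that catchment totals will separate the randomised conditions, but it does propose to judge from them whether the interventions improved uptake.

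The conclusion survives. The missing baseline and the non-random choice of counties follow from the text. The other readings do not repair the test. Lower coverage makes it more sensitive to chance gaps, and coverage of 60% leaves the thresholds almost unchanged. The test holds its 5% level only if counties are practically identical.

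**Conclusion.** The concern holds. Applied as written, the county chi-square can report a pre-existing or chance difference between county groups as benefit or as harm, and it cannot show that coverage rose. If counties differ by an SD of about 1 point or more, a significant result with no effect is more likely than not in nearly all the settings tried. A plausible effect among participants would lie below the threshold. The rates rest on assumed county numbers, sizes and SDs. The absence of a baseline and of county randomisation needs no assumption.

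The randomised primary analysis and the randomised uptake comparison are not affected. The change should be made because the result would otherwise stand as a prespecified statement about uptake.

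**What to change.** **Section I.** Replace the chi-square with each county's change in coverage, using the same dose measure and data source throughout. Use one calendar window for all counties, for example from before the first event to 60 days after the last. A common window is needed because events are scheduled as they arise and comparison counties have no dates of their own. Make the county the unit, with an unweighted two-sample t-test, a permutation test, or an unweighted regression adjusted for pre-period coverage. Do not use population-weighted regression with ordinary robust errors. Define a study county by event location, and report the share of participants who live in one; county of residence is already collected. Label the result descriptive and ecological, because a county-level test of change does not remove bias if the choice of counties is linked to their trend.

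**Section D, Evaluation.** Reword so that any claim that the interventions improved uptake rests on the planned randomised comparison at 30 and 60 days, with catchment data as context only.

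**Cost.** Two changes of wording and one earlier extract of the same public data, provided that the chosen dose measure is available for that date. Intervals become wider. With an assumed SD of change of 1 point, the county t-test has 80% power only for 1.03 points (9 of 60 counties) or 0.89 points (12 of 80), far above the 0.02-0.05 points expected from participants. That is a further reason for the descriptive label.
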